**Diagnostic performance of a rapid ultrafiltration test to
assess preload dependence in critically ill patients treated
with continuous renal replacement therapy.**

UF CHALLENGE Study

**This is a translation from the original French document.
In case of discrepancy, the original French version shall prevail.**

The publication of results related to this protocol can be found at:
<https://ccforum.biomedcentral.com/articles/10.1186/s13054-025-05674-3> (Biscarrat et al. 2025 Critical Care)

Sponsor

Hospices Civils de Lyon
[name]
[name]
[name]

Principal Investigator

[name]
Intensive Care Medicine – Critical Care Unit
Hôpital de la Croix Rousse, GHN
[name]
[name]
Email: [contact]
[contact]

Protocol Version

Version 02 – March 16, 2022

SUMMARY

Background / Rationale

A positive fluid balance is a risk factor associated with increased mortality in intensive care (Vaara et al. 2012, *Critical Care*). Continuous renal replacement therapy (CRRT) is an effective means of regulating fluid overload in patients with acute kidney injury in critical care settings. However, this organ support technique may induce episodes of hemodynamic instability. Such episodes often lead to discontinuation of fluid removal during CRRT, although these events are not necessarily associated with cardiac preload dependence (Bitker et al. 2016, *Crit Care*; Chazot et al. 2021, *Crit Care*). Therefore, the causal link with ultrafiltration is not always certain, and fluid removal could potentially be continued.

Currently, the best means of identifying a preload-dependent hemodynamic profile is a postural maneuver (passive leg raise or Trendelenburg), which is a validated test for assessing the impact of insufficient venous return on cardiac output (Monnet et al. 2016 *Intensive Care*; Yonis et al. 2017 *Crit Care Med*). However, these maneuvers only identify patients who are *already* preload-dependent. To date, no clinical test is available to identify patients at risk of becoming preload-dependent and thus suffering the deleterious consequences of inappropriate fluid removal.

We aim to evaluate a novel predictive test based on a rapid ultrafiltration challenge, which could reveal a patient's transition into preload dependence. Validation of this test would allow adjustment of net ultrafiltration (fluid removal) according to the hemodynamic response in terms of cardiac preload.

Primary Objective

To assess the diagnostic performance of a rapid ultrafiltration test (without distinguishing between 15- and 30-minute trials) in detecting preload dependence in critically ill patients treated with continuous renal replacement therapy, by quantifying the change in cardiac index induced by the test and comparing it to that induced by a postural maneuver (reference standard) performed after the ultrafiltration test.

Secondary Objectives

- To assess the diagnostic performance of the 15-minute and 30-minute rapid ultrafiltration tests, respectively, using the same methodology.
- To determine the optimal threshold of cardiac index variation that defines preload dependence for each test (pooled and separately), with calculation of sensitivity, specificity, positive and negative predictive values.
- To compare the diagnostic performance of ultrafiltration tests (pooled and separate) with that of the pre-test postural maneuver.
- To compare the diagnostic performance between the 15-minute and 30-minute tests.
- To evaluate the impact of ultrafiltration tests on additional hemodynamic variables (absolute values and relative changes from baseline): central venous pressure, heart rate, mean and pulse arterial pressure, extravascular lung

water, pulmonary vascular permeability index, and global end-diastolic volume index.

- To assess the ability of ultrafiltration tests (pooled and separate) to predict hemodynamic instability with preload dependence occurring within 8 hours following the test.

Methodology / Study Design

- Pilot study
- Physiological, prospective, single-center, open-label
- Sequential crossover design with sealed-envelope randomization of intervention order
- Diagnostic test evaluation (rapid ultrafiltration challenge)

Primary Endpoint

Diagnostic performance of a rapid ultrafiltration test (regardless of duration), assessed by the area under the ROC curve (receiver operating characteristics) of cardiac index variation compared to the reference measurement (postural maneuver performed after the test).

Secondary Endpoints

- Diagnostic performance of the 15-minute and 30-minute rapid ultrafiltration tests, assessed by ROC analysis of cardiac index variation and comparison with the reference maneuver.
- Optimal thresholds (and 95% CI) of cardiac index variation for each test, determined using the Youden index, with associated sensitivity, specificity, PPV, and NPV.
- Comparative diagnostic performance of ultrafiltration tests (pooled and separate) versus pre-test postural maneuver, and between tests (15 vs. 30 minutes).
- ROC AUC values compared using DeLong's method.
- Hemodynamic variables measured by cardiac output monitoring (CVP, HR, MAP, pulse pressure, EVLW, PVPI, GEDVi), analyzed as absolute values and changes from baseline, correlated with cardiac index variation.
- Incidence of hemodynamic instability (tachycardia, hypotension, decreased cardiac index, mottling) within 8 hours after the ultrafiltration test.

Target Population

Adult ICU patients (under mechanical ventilation and sedation) with acute kidney injury (KDIGO stage 3) requiring continuous renal replacement therapy initiated within the past 14 days.

Sample Size

N = 20 evaluable patients, each undergoing 2 tests → total of 40 rapid ultrafiltration challenges.

Study Duration

- Inclusion period: 18 months
- Maximum participation per patient: 72 hours
- Total study duration: 18 months + 3 days

Expected Outcomes

The current reference dynamic test (passive leg raise or Trendelenburg) remains imperfect in assessing tolerance to fluid removal during CRRT, with sensitivity <80%. The UF challenge may prove more sensitive, particularly in patients at the borderline between the ascending and plateau phases of the Frank-Starling curve. This simple, dynamic, low-cost test could help clinicians individualize ultrafiltration prescriptions, avoid deleterious hypotension, and rapidly integrate into clinical practice. Currently, no specific dynamic test exists to evaluate the safety and efficacy of fluid removal in this population.

GENERAL INFORMATION

Title: Diagnostic performance of a rapid ultrafiltration test to assess preload dependence in critically ill patients treated with continuous renal replacement therapy.

Project Identifiers and Update History

- Sponsor Code: 69HCL21_1250
- ClinicalTrials.gov registration number: NCT05214729
- CPP Sud-Est VI favorable opinion date: XX/XX/XXXX

Version History

Version	Date	Reason for Update
1	02/11/2021	Initial draft
2	16/03/2022	Comments from CPP

Sponsor

Identity: Hospices Civils de Lyon

[name]

[name] [name]

Signature of the protocol on behalf of the Sponsor:

[name], Director of Health Research

Hospices Civils de Lyon, Health Research Directorate,

Administrative Headquarters,

[name],

[name],

[name]

[contact]

Currently, the most reliable tool for diagnosing preload dependence is a dynamic test: passive leg raise (supine) or Trendelenburg (prone) with continuous cardiac output monitoring. A $\geq 10\%$ increase in cardiac output indicates preload dependence. Studies, including work by our team, confirm sensitivity and specificity $>85\%$. This test performs well to identify patient who are preload-dependent, and who are consequently at higher risk of preload-dependent hypotension. Yet, in preload-independent patients (i.e. those with a negative passive leg raising test, no validated predictive test exists for ultrafiltration-related hypotension in relation with their switch to a preload-dependent status.

Research Hypothesis

A 250 mL rapid ultrafiltration challenge (15 or 30 minutes) may help identify preload-independent patients at risk of becoming preload dependent during CRRT

Justification of Methodological Choices

- Sequential crossover design: each patient serves as their own control, limiting variability.
- Randomization of challenge order prevents bias.
- 250 mL volume chosen as it mimics passive leg raise (~300 mL).
- Two rates (15 vs. 30 minutes) tested to assess the effect of ultrafiltration kinetics and plasma refilling.

The PiCCO® Monitoring Device

The device combines transpulmonary thermodilution and pulse contour analysis for continuous cardiac output and displays advanced hemodynamic parameters (extravascular lung water, pulmonary vascular permeability index, global end-diastolic volume index).

Benefit/Risk Assessment

- Benefit: collective, through validation of a new predictive test.
- Risk: minimal, transient hemodynamic instability possible
- No additional invasive procedures required.

Expected Outcomes

A UF challenge may have higher diagnostic performance than the passive leg raising test to identify patients at the transition between preload independence and dependence. It is simple, dynamic, inexpensive, and potentially useful in guiding ultrafiltration in CRRT patients.

RESEARCH OBJECTIVES

Primary Objective

To evaluate the diagnostic performance of a rapid ultrafiltration challenge (250 mL over 15 or 30 minutes) in detecting preload dependence in preload independent critically ill patients treated with continuous renal replacement therapy.

Diagnostic accuracy will be assessed by the change in calibrated cardiac index induced by the ultrafiltration challenge compared with the reference postural maneuver (passive leg raise or Trendelenburg) performed *after* the challenge.

Secondary Objectives

1. To evaluate separately the diagnostic performance of the 15-minute and 30-minute UF challenges.
2. To determine the optimal threshold of calibrated cardiac index variation defining preload dependence for each test (pooled and separate), with sensitivity, specificity, PPV, and NPV.
3. To compare diagnostic performance of UF challenges (pooled and separate) with that of the pre-test postural maneuver.
4. To compare diagnostic performance between the 15-minute and the 30-minute challenges.
5. To assess the effect of ultrafiltration challenges on other hemodynamic parameters (absolute values and relative changes from baseline): central venous pressure (CVP), heart rate (HR), mean arterial pressure (MAP), pulse pressure, extravascular lung water (EVLW), pulmonary vascular permeability index (PVPI) and global end-diastolic volume index (GEDVi)
6. To evaluate the ability of ultrafiltration challenges to predict hemodynamic instability with preload dependence within 8 hours after the test.

STUDY DESIGN / METHODOLOGY

Type of Research

- Pilot study
- Physiological, prospective, single-center, open-label
- Sequential crossover design with randomization of challenges' order
- Diagnostic test evaluation

Study Population

Inclusion Criteria

- Adults ≥ 18 years hospitalized in the ICU
- Mechanical ventilation and sedation
- Acute kidney injury KDIGO stage 3
- CRRT initiated < 14 days before inclusion
- With a calibrated continuous cardiac index monitoring device in place (PiCCO®, Pulsion Medical, Feldkirch, Germany)

- Informed consent (patient or representative)

Exclusion Criteria

- Arterial lactate > 4 mmol/L
- Calibrated cardiac index < 2 or > 4 L/min/m²
- Preload dependence identified within the preceding 2 hours
- ECMO
- Acute hemorrhage
- End stage chronic kidney disease or renal graft recipient
- Acute stroke with coma
- Fulminant hepatitis
- Inability to perform PLR: amputation, inferior vena cava obstruction, abdominal compartment syndrome
- Pregnancy or breastfeeding
- Imminent death
- Decision of withholding of care
- Patients under legal protection (guardianship, trusteeship, detention)
- Already included in the study

Number of Patients

- 20 patients included
- Each patient undergoes 2 ultrafiltration challenges (15- and 30-minute, in randomized order)
- Total: 40 evaluable challenges

Randomization

- Randomized order determined by sealed envelope method
- Each patient serves as their own control

Blinding

- Not feasible given the study design

Co-interventions

Recommendation for not changing any of the following parameters, prescription or settings during the trial's interventions:

- Sedation
- Mechanical ventilation
- Vasopressor and inotrope support
- Fluid bolus therapy or transfusion

Study Procedures

1. Baseline data collection (demographics, clinical scores, renal data, hemodynamics)

2. Calibration of the monitoring device and pre-test postural maneuver (PLR or Trendelenburg) during 1 minute with collection of the relative change in continuous cardiac index
3. Ultrafiltration challenge: 250 mL over 15 or 30 minutes (randomized), by setting a UF flow of 1000 ml/h or 500 ml/h, respectively
4. Re-calibration of the monitoring device and post-test postural maneuver (reference standard, PLR or Trendelenburg) during 1 minute with collection of the relative change in continuous cardiac index
5. Repeat sequence for second challenge after a wash-out period of 24h (cross-over design)
6. Follow-up: monitoring for 8 hours post-test for instability

Data Collected

- Demographics: age, sex, weight, height
- Clinical: history, reason for ICU admission, severity scores (SAPS II, SOFA)
- Renal: CRRT indication and parameters
- Hemodynamics: CI, CVP, HR, MAP, PP, EVLW, PVPI, GEDVi (before/after each step), vasopressor dosage
- Ventilatory settings: VT, PEEP, FiO₂, arterial blood gas results
- Results of the pre and post-test postural maneuvers
- Any severe and non-severe adverse events

ENDPOINTS / EVALUATION CRITERIA

Primary Endpoint

The diagnostic performance of the rapid ultrafiltration challenge (pooled 15- and 30-minute tests).

- Performance assessed by the area under the ROC curve (AUC) of cardiac index variation.
- Reference: continuous cardiac index relative variation induced by the post-test postural maneuver performed after the challenge.

Secondary Endpoints

1. Respective diagnostic performance of the 15-minute and 30-minute challenges (ROC AUC).
2. Determination of the optimal threshold of cardiac index variation (Youden index) with sensitivity, specificity, PPV, and NPV.
3. Comparative performance of challenges (pooled and separate) versus the pre-test postural maneuver.
4. Comparison of diagnostic performance between the 15-minute and 30-minute challenges ROC AUCs compared using DeLong's test.
5. Analysis of additional hemodynamic parameters: CVP, HR, MAP, Pulse pressure, EVLW, PVPI and GEDVi (absolute values and relative changes, correlated with cardiac index variation).

6. Incidence of hemodynamic instability within 8 hours post-test (tachycardia, hypotension, decreased CI, mottling).

Study duration

- Inclusion period: 18 months
- Maximum participation per patient: 72 hours
- Total study duration: 18 months + 3 days

Sample size

- 20 patients planned.
- Each undergoes 2 ultrafiltration challenges (15- and 30-minute, randomized).
- Total: 40 evaluable ultrafiltration challenges.

The sample size was chosen pragmatically, consistent with the pilot/exploratory nature of the study.

STUDY PROCEDURES AND CONDUCT

Overall Study Flow

1. Screening and Inclusion
 - Verify inclusion and exclusion criteria.
 - Provide information to patient or legally authorized representative; obtain consent in compliance with French law.
2. Baseline Assessment
 - Collect demographics and clinical data (age, sex, weight, height, SAPS II, SOFA, reason for ICU admission, history).
 - Record renal data (CRRT indication and parameters, time since CRRT initiation).
 - Baseline hemodynamic measurements: CI, CVP, HR, MAP, PP, EVLW, PVPI, GEDVi, vasopressor dosage
 - Mechanical ventilation settings
3. Randomization
 - Determine challenge sequence (15 vs 30 minutes) using sealed envelopes.
4. Pre-test postural maneuver
 - Passive leg raise (supine) or Trendelenburg (prone).
 - Record hemodynamic parameters before and during maneuver.
5. Ultrafiltration Challenge
 - Remove 250 mL with UF over 15 or 30 minutes.
 - Monitor CI and hemodynamic parameters continuously.
 - Record parameters at the end of challenge.
6. Post-test Postural Maneuver (Reference)
 - Repeat maneuver (PLR or Trendelenburg).
 - Record hemodynamic parameters before and during maneuver.
7. Follow-up
 - Any hemodynamic instability episodes occurring over the following 8h

8. Second Ultrafiltration Challenge

- After a 24h wash-out period, repeat procedure with the alternate duration (30 or 15 minutes).
- Same sequence: pre-test maneuver → challenge → post-test maneuver.

9. Follow-up

- Monitor for 8 hours post-challenges.
- Record any hemodynamic instability.

Data Management

- Data recorded in a secure **electronic case report form (eCRF)**.
- Source documents: ICU medical files, CRRT charts, PiCCO® data, nursing observation sheets.
- Data entry performed by investigators, validated and monitored by sponsor.

Safety Monitoring

- Continuous monitoring of cardiac output and hemodynamics during challenges.
- **Adverse events (AEs) and serious adverse events (SAEs)** recorded and reported.
- Risks: transient hypotension or tachycardia, reversible and clinically manageable.

Premature Discontinuation

Patients may be withdrawn if:

- Consent withdrawn.
- Serious adverse event occurs.
- Investigator deems it in patient's best interest.
- Limitation of therapeutic effort decided.
- Technical impossibility (e.g., PiCCO® failure, CRRT interruption).

SAFETY EVALUATION AND RISK MANAGEMENT

Potential Risks for Participants

- The ultrafiltration challenge consists of removing 250 mL of ultrafiltrate over 15 or 30 minutes.
- Main anticipated risk: transient hemodynamic instability, such as hypotension, tachycardia, decreased cardiac index, or mottling.
- These events are expected to be limited, reversible, and continuously monitored with PiCCO® cardiac output monitoring.
- No additional invasive procedure is required beyond standard ICU monitoring.

Adverse Events (AEs) and Serious Adverse Events (SAEs)

- Adverse Event (AE): any unfavorable or unintended medical occurrence during research, whether or not related to the investigational procedure.

- Serious Adverse Event (SAE): an event that results in death, is life-threatening, requires or prolongs hospitalization, results in significant disability, or is deemed medically significant by the investigator.

Collection and Reporting

- All AEs and SAEs occurring from the start of ultrafiltration challenges until 8 hours post-procedure will be documented in the eCRF.
- The investigator will assess causality (related or not to the ultrafiltration challenge).
- SAEs must be reported to the sponsor within 24 hours of investigator awareness.
- The sponsor will notify relevant authorities (CPP, ANSM if applicable) in compliance with French regulations.

Measures for Participant Safety

- Continuous monitoring ensures early detection of instability.
- If instability occurs (e.g., MAP <60 mmHg, sustained tachycardia, cardiac index decrease >20%), the ultrafiltration challenge will be immediately stopped, and corrective treatment administered (fluids, vasopressors, etc.).
- The investigator may withdraw the patient from the study in case of unacceptable risk.

STATISTICAL ANALYSIS

General Principles

- Analyses performed using R software (latest version available).
- Two-sided significance level set at 0.05.
- 95% confidence intervals reported.
- Analyses conducted on the intention-to-treat and per-protocol population (patients with at least one evaluable ultrafiltration challenge).

Primary Analysis

- The primary endpoint is the diagnostic performance of the ultrafiltration challenge (15- and 30-minute tests pooled).
- Performance assessed by calculating the area under the ROC curve (AUC) of cardiac index variation compared with the post-test postural maneuver.
- AUC values will be reported with 95% confidence intervals.

Secondary Analyses

1. Diagnostic performance of the 15-minute and 30-minute ultrafiltration challenge alone (ROC AUC).
2. Determination of the optimal threshold of cardiac index variation (Youden index) defining preload dependence, with sensitivity, specificity, PPV, and NPV.
3. Comparative diagnostic performance of ultrafiltration challenges (pooled and separate) versus the pre-test postural maneuver, compared using the

respective ROC AUCs of 15-minute and 30-minute challenges using DeLong's test.

4. Analysis of additional hemodynamic parameters (CVP, HR, MAP, PP, EVLW, PVPI, GEDVi) in absolute values and relative changes from baseline, correlated with cardiac index variation using Pearson or Spearman correlation.
5. Description of the incidence of hemodynamic instability within 8 hours post-test, expressed as proportions with 95% confidence intervals.

Handling of Missing Data

- Missing data will not be imputed.
- Analyses will be based on available data.
- The extent and reasons for missing data will be described.

Interim Analysis

No interim analysis is planned.

QUALITY ASSURANCE, ETHICS, AND DATA MANAGEMENT

Regulatory and Ethical Aspects

- The study will be conducted in compliance with the Declaration of Helsinki (2013 version) and the principles of Good Clinical Practice (ICH E6 R2).
- The protocol, patient information, and consent form have been submitted to and approved by the CPP Sud-Est VI (Comité de Protection des Personnes).
- The study has been declared to the CNIL (Commission Nationale de l'Informatique et des Libertés) in accordance with French law and the General Data Protection Regulation (GDPR, EU 2016/679).
- Any substantial protocol amendments will be submitted for approval to the CPP and, if necessary, to the French National Agency for Medicines and Health Products Safety (ANSM).

Informed Consent

- Informed consent must be obtained from each participant or their legally authorized representative before any research-specific procedure.
- If the patient regains decision-making capacity, consent will be sought again for continuation.
- Consent procedures comply with the French Jardé Law for research involving human subjects.

Confidentiality and Data Protection

- Participant data will be coded with a unique study identifier.
- Only authorized members of the research team and sponsor will access identifiable data.
- Data will be securely stored in a password-protected electronic case report form (eCRF).

- In compliance with GDPR and French law, participants may access, rectify, or delete their data by contacting the sponsor.

Monitoring and Quality Assurance

- The sponsor's Clinical Research Unit (Hospices Civils de Lyon) will conduct monitoring visits to ensure compliance with the protocol and regulatory requirements.
- Source data verification will be performed to ensure consistency between medical records and eCRF entries.
- Monitoring activities will be documented in formal monitoring reports.

Archiving

- Essential study documents (protocol, CRFs, monitoring reports, patient files, consent forms) will be archived for 15 years after study completion.
- Electronic data will also be securely stored by the sponsor for the same duration.

Insurance

- The sponsor has subscribed to an insurance policy covering the civil liability of investigators and institutions involved, in accordance with Article L.1121-10 of the French Public Health Code.

Publication and Communication of Results

- Results will be submitted for publication in a peer-reviewed international scientific journal.
- Authorship will follow the criteria defined by the International Committee of Medical Journal Editors (ICMJE).
- Negative or inconclusive results will also be published.
- Results may be presented at national and international scientific meetings.

REFERENCES

1. Vaara ST, et al. Fluid overload is associated with increased mortality in critically ill patients with acute kidney injury. *Crit Care*. 2012;16:R197.
2. Wiedemann HP, et al. Comparison of two fluid-management strategies in acute lung injury. *N Engl J Med*. 2006;354(24):2564-2575.

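### The reference maneuver is obtained after the challenge result has been seen, and the plan sets blinding aside in one line without protecting how the reference is read

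*Combined protocol and SAP*

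**What the plan says.** All places are in the combined protocol and SAP.

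- **Blinding** (Study Design / Methodology): the full text is "Not feasible given the study design". The Type of Research list describes the study as "Physiological, prospective, single-center, open-label".
- **Sequence** (Overall Study Flow, items 5 and 6): during the challenge staff are to "Monitor CI and hemodynamic parameters continuously" and then "Record parameters at the end of challenge". The post-test maneuver is the next step, with values taken before and during it.
- **Safety** (Measures for Participant Safety): the stopping provision refers in part to a "cardiac index decrease >20%), the ultrafiltration challenge will be immediately stopped", so CI has to be visible at the bedside.
- **Reference** (Study Procedures, item 4): after re-calibration, the maneuver is held "during 1 minute with collection of the relative change in continuous cardiac index". The primary analysis is the ROC AUC of the challenge-induced CI variation against this result.
- **Cut-off**: an increase of at least 10% is given as the sign of preload dependence in the background text before Research Hypothesis. The endpoint and statistics sections do not repeat it.
- **Data** (Data Management): "Data entry performed by investigators, validated and monitored by sponsor". Also: "Source documents: ICU medical files, CRRT charts, PiCCO® data, nursing observation sheets".

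**The concern.** The Blinding line treats two things as one. The first is whether staff can be kept unaware of the challenge and its CI response while it runs. They cannot. The second is whether the reference can be read and classified without knowledge of that response. The plan never considers this.

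The second question matters because the reference is a percentage change in a continuously displayed signal, split at a threshold, and the plan leaves open which baseline and which value in the minute define the change. At the entry CI range of 2 to 4 L/min/m², one percentage point is 0.02 to 0.04 L/min/m², so a modest difference in the values chosen can move a borderline reading across 10%.

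If such choices lean toward the challenge result, agreement between the two tests rises, and that agreement is the primary endpoint. The planned 95% confidence interval reflects sampling error only and would not reveal the shift.

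**Working it through.** **1. What the text establishes.** The plan's only sizing figure reproduces: 20 patients × 2 challenges = 40. The order of steps is CI watched, CI recorded, re-calibration, reference maneuver. The challenge result is therefore known at the bedside before the reference exists. No section specifies a reader, a baseline window, a choice of peak or mean, or a masked derivation.

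**2. How many readings are borderline.** The documents give no distribution for the reference response, so these inputs are assumptions: normal, mean μ = 6 or 7%, SD σ = 5 or 6 points. The share within ±d points of the 10% cut-off is

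Φ((10 + d − μ)/σ) − Φ((10 − d − μ)/σ).

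For μ = 6, σ = 5:

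- d = 1: Φ(1.0) − Φ(0.6) = 0.841 − 0.726 = 0.116
- d = 2: Φ(1.2) − Φ(0.4) = 0.885 − 0.655 = 0.230

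Over the four combinations of μ and σ, the share is 11–13% for ±1 point and 21–26% for ±2 points.

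**3. Effect on the AUC.** Further assumptions: correlation between challenge response and reference response of 0.4 or 0.6 (undistorted AUC about 0.69–0.70 or 0.79–0.80), and a fraction of borderline readings classified to agree with the challenge result. The plan gives staff no challenge cut-off. The value above which the challenge was taken to suggest a positive reference was therefore varied, from its mean to the quantile matching the reference prevalence. There were one million simulated pairs per combination of mean, SD and correlation.

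| Band around 10% | Fraction steered | Rise in AUC | Labels changed, of 40 |
|---|---|---|---|
| ±1 point | a quarter | 0.01–0.02 | 0.5–0.7 |
| ±1 point | a half | 0.02–0.04 | 1.0–1.3 |
| ±2 points | a quarter | 0.02–0.03 | 0.9–1.3 |
| ±2 points | a half | 0.04–0.07 | 1.9–2.5 |

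The smallest rise was 0.792 to 0.803 (μ = 6, σ = 6, correlation 0.6). The largest was 0.697 to 0.765 (μ = 6, σ = 5, correlation 0.4).

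**4. Scale against sampling error.** The Hanley–McNeil formula, treating the 40 challenges as independent, is

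SE² = [A(1 − A) + (n₁ − 1)(a − A²) + (n₀ − 1)(b − A²)]/(n₁n₀), with a = A/(2 − A) and b = 2A²/(1 + A).

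At A = 0.80, a = 0.667 and b = 0.711.

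- 20 positive, 20 negative: SE² = (0.160 + 0.507 + 1.351)/400 = 0.00504; half-width 1.96 × 0.071 = 0.14
- 10 positive, 30 negative: SE² = (0.160 + 0.240 + 2.062)/300 = 0.00821; half-width 1.96 × 0.091 = 0.18

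The possible shift is smaller than the sampling uncertainty. It is systematic, however, and would not average out with more patients.

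**The case against.** The case on the other side has several parts.

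- **The plan is partly right.** Bedside staff must see CI while a CI-based stopping provision applies, so the challenge and the performance of the maneuver cannot be masked. This stands, and it confines the point to reading and classification.
- **The reference is a device reading.** It follows re-calibration, entries are validated by the sponsor, and source data verification is planned under Monitoring and Quality Assurance. These steps limit discretion over what is entered. They check transcription, though, not which of several genuine values was chosen.
- **Staff have no challenge cut-off.** The threshold is found afterwards by the Youden index, so staff see a continuous change with no positive or negative label. This stands and weakens any steering. If only challenge results more than 1 SD from their mean influence the reader, the case with ±2 points and half steered gives a rise of 0.02–0.03.
- **This is a pragmatically sized pilot.** That explains the wide interval. It is not a reason to leave the reference undefined, since defining it costs only text.

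A reader might also infer that one investigator performs the challenge, runs the maneuver, picks the values and enters the percentage. The documents assign none of these roles beyond data entry. Nor do they show that masked derivation from the PiCCO® record is certainly possible: PiCCO® data are listed as a source, but a stored continuous trace, time stamps and export are not described.

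**Conclusion.** The point holds for the reading of the reference. The challenge result is known before the reference is obtained, and the plan neither fixes how the reference value is extracted nor considers deriving it without that knowledge. The possible rise in the primary AUC is about 0.01 to 0.07, with roughly one to two of 40 labels changed in most of the cases run. It rests wholly on assumed values for the mean, SD, correlation, borderline band and fraction steered.

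A reader might go further and infer that the reported AUC will be biased upward. The documents do not support that. The calculation shows how sensitive the endpoint is if readings are steered; it gives no evidence that they are. The change should be made because it is cheap and protects the primary endpoint, not because an error has been shown.

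**What to change.** Keep the challenge and the CI-based safety monitoring open-label, as planned. Replace the Blinding line with text along these lines:

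> The challenge is open-label. The CI change during each postural maneuver is derived by a pre-specified rule that states the baseline window, whether the peak or the mean within the 1-minute maneuver is used, and the ≥10% cut-off. Where the time-stamped PiCCO® record can be exported, the rule is applied by script to maneuver segments coded without challenge order or challenge result, and the derived values are used in the primary ROC analysis. Where it cannot be exported, the same rule is applied to the recorded before and during values, and unmasked reading is reported as a limitation.

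Repeat the rule and the cut-off in the Primary Endpoint and Primary Analysis sections.

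The cost is a few lines of protocol, a script, and time-stamped export or event marking at the bedside. No extra patient procedure is needed. The fixed rule does most of the work, because it removes the choice of value whoever applies it; coding the segments adds protection where traces exist. Two sources of error remain and should be acknowledged: how unmasked staff perform the maneuver, and any error shared between the end-of-challenge CI and the baseline of the maneuver that follows.
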